# 9.7 Medication Handling Irregularities (MHIs) and Events Subject to Additional Monitoring (ESAMs)

MHIs and ESAMs will be summarized for the Safety Sample by treatment group and overall. By-patient listings will be provided.

## 9.8 Concomitant Medications

Number and proportion of patients taking concomitant medications prior to the open-label treatment phase, during the open-label treatment phase, and after study therapy are tabulated by

drug classification using the World Health Organization (WHO) drug dictionary for the Safety Sample.

#### 9.9 Extent of Exposure

The start date of the open-label study therapy - centanafadine - will be the first day of dosing during the open-label treatment phase. The number and percentage of patients who receive study medication during the open-label treatment phase, will be presented by week. Each dosing week will be based on the actual week; i.e., Day 1-7 in Week 1, Day 8-14 in Week 2, etc. This summary will be performed on the Safety Sample.

The mean daily dosage will be summarized by week using descriptive statistics. The mean daily dosage per patient per week will be determined for each week of the study. This will be calculated by dividing the sum of individual total doses by the number of days in the week interval. The summary will contain the number of patients receiving study medication during the open-label treatment phase, and the mean and range of the mean daily dose for each week

## **10** Conventions

#### 10.1 Study Visit Windows

Study visit windows will be used to map visits using study day intervals. This visit window convention applies to tables and listings for all efficacy and safety scales (AISRS, CGI-S, AIM-A, CGI Change from Baseline, CCI). This derived study window variable will be named as WEEK and will be footnoted. In listings it will be listed along with the eCRF study visit.

Table 10-1 shows classifications for study day intervals in the open-label treatment period. The variable "target day" is defined using the number of days since the start of open-label dosing in the open-label treatment period. The first day of open-label dosing is defined as "Day 1".

If more than one observation falls within a particular study day interval, then the last observation within that interval is used. Evaluations occurring more than three days after the last open-label dosing date and evaluations occurring during the follow-up period will not be mapped into study visit windows and will be excluded from the open-label treatment period analysis.

Week	Target Day a	Study Day Interval a
1	7	2-10
2	14	11-21
4	28	22-42
8	56	43-70
12	84	71-98
16	112	99-126
20	140	127-161
26	182	162-203
32 °	224	204-245
38 °	266	246-287
44 °	308	288-336
52 °	364	337-385 b

Table	10-1:	Study	Day an	d Visit	Windo	ows in t	the O	pen-label	Treatment	Period
			•							

a Relative to the first day of open-label IMP in the open-label treatment period.

**b** Evaluations occurring more than three days after the last open-label dosing date and evaluations occurring during the follow-up period will be excluded from the open-label treatment period analyses.

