## 9 Safety Analysis

The primary safety endpoint analysis is the frequency and severity of AEs in the open-label treatment period (see Section 9.1). Other standard safety variables to be analyzed include clinical laboratory tests, vital signs, body weight, waist circumference, BMI, 12-lead electrocardiograms (ECGs), and physical examinations. In addition, data from the following safety scales will be evaluated: C-SSRS and Study Medication Withdrawal Questionnaire (SMWQ).

Safety analyses will be conducted based on the Safety Sample, and summary statistics will be provided by parent study treatment group for rollover subjects, de novo subjects and overall, unless otherwise indicated.

Unless otherwise specified, in general, analysis of safety data will be performed on observed case and for last visit.

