#### 9.5 Suicidality Data

Suicidality will be monitored during the study using the C-SSRS and will be summarized as number and percentage of subjects reporting any suicidal behavior, ideation, behavior by type (4 types), ideation by type (5 types) and treatment emergent suicidal behavior and ideation. Summary will be provided for the open-label treatment period for the Safety Sample.

Suicidality is defined as report of at least one occurrence of any type of suicidal ideation or at least one occurrence of any type of suicidal behavior during assessment period (count each person only once).

Treatment emergent suicidal behavior and ideation is summarized by four types: Emergence of suicidal ideation, Emergence of serious suicidal ideation, Worsening of suicidal ideation, Emergence of suicidal behavior.

Emergence of suicidal behavior/ideation is defined as report of any type of suicidal behavior/ideation during treatment when there was no baseline suicidal behavior/ideation.

Emergence of serious suicidal ideation is defined as observation of suicidal ideation severity rating of 4 or 5 during treatment when there was no baseline suicidal ideation.

Worsening of suicidal ideation is defined as a suicidal ideation severity rating that is more severe than it was at baseline.

For the open-label treatment period analyses, the last available measurement prior to the first dose of open-label IMP is being used as "Baseline".

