# 10.2.5 Columbia-Suicide Severity Rating Scale (C-SSRS)

Suicidality will be monitored during the trial using the C-SSRS. The C-SSRS is a semistructured interview that captures the occurrence, severity, and frequency of suicide-related thoughts and behaviors during the assessment period. The interview includes definitions and suggested questions to solicit the type of information needed to determine if a suicide-related thought or behavior has occurred. The interview and rating for the C-SSRS must be completed by a licensed clinician who has been successfully trained to rate this scale by the sponsor or a designee and is medically responsible for the subject. Documentation of trial training should be maintained in the investigational site's files.

This trial will use the "Baseline/Screening" and "Since Last Visit" versions of the scale. The "Baseline/Screening" version, which assesses the life-time experience of the subject with suicide events and suicidal ideation and the occurrence of suicide events or ideation within a specified time period prior to entry into the trial, will be completed for all de novo subjects at the screening visit to determine the eligibility. Any subject with active suicidal ideation within the last 30 days, suicidal behaviors within the last year, or who in the clinical judgment of the investigator presents a serious risk of suicide should be excluded from the trial. The "Since Last Visit" C-SSRS form will be completed at all other in-clinic visits for all subjects (rollover and de novo).

The C-SSRS is assessed at each scheduled visit in the screening period (for de novo subjects), the open-label treatment period and at 2 and 7 days after the last dose of IMP in the follow-up period.

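### Day 2 and Day 7 follow-up C-SSRS forms enter no planned C-SSRS table, and the visit-window rule also drops an early-termination form taken more than 3 days after the last dose, although that form looks back over dosing days.

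*SAP*

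**What the plan says.** SAP 10.1 sets the scope of the visit windows: "This visit window convention applies to tables and listings for all efficacy and safety scales". The same section sets the cut-off: "Evaluations occurring more than three days after the last open-label dosing date and evaluations occurring during the follow-up period will not be mapped" into visit windows, and they "will be excluded from the open-label treatment period analysis". Footnote b of Table 10-1 repeats the exclusion.

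SAP 9 places the C-SSRS in that class: "data from the following safety scales will be evaluated: C-SSRS", alongside the SMWQ. SAP 9.5 then fixes the reporting period for suicidality: "Summary will be provided for the open-label treatment period for the Safety Sample". It defines emergence as "report of any type of suicidal behavior/ideation during treatment when there was no baseline suicidal behavior/ideation".

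Collection runs longer than reporting. SAP 10.2.5 and Protocol Tables 3.7-2 and 3.7-4 schedule the C-SSRS at treatment visits and also "at 2 and 7 days after the last dose of IMP in the follow-up period". After screening, every in-clinic visit uses the Since Last Visit version (Protocol 3.7.4.6.2).

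**The concern.** This is a 52-week safety trial, and suicidality is one of its named safety assessments. Two sets of collected forms appear to be left out of the C-SSRS outputs.

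- **Follow-up forms.** They cover the days just after stopping the drug, the same days for which the SAP does report withdrawal symptoms.
- **Late early-termination forms.** A cut-off in days since the last dose suits a score of current state, such as the AISRS. The Since Last Visit C-SSRS is retrospective. Its completion date says little about when an event happened, so a form dated after the cut-off can report an event that occurred on drug.

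The second loss falls only on subjects who stopped dosing and were seen late. In an any-occurrence count, leaving a form out can keep the number of subjects with an event the same or lower it, but cannot raise it.

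**Working it through.** The plan states no figure on this point, so the check sets the sections side by side and counts forms and days.

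**1. Scheduled C-SSRS forms after the first dose** (Protocol Tables 3.7-1 to 3.7-4)

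- Treatment: Weeks 1, 2, 4, 8, 12, 16, 20, 26, 32, 38, 44 and 52/ET, which makes 12. Week 48 has none.
- Follow-up: Days 2 and 7, which makes 2.
- Follow-up share: 2 / (12 + 2) = 2/14 = 14.3%.

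**2. Where the follow-up forms go**

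- Day 2 has a window of +1 day, so it falls 2 to 3 days after the last dose. It passes the 3-day limit and is excluded only because it belongs to follow-up.
- Day 7 has a window of +2 days, so it falls 7 to 9 days after the last dose. It is excluded on both grounds.
- None of the titles CT-6.1 to CT-6.8 names follow-up. SAP 9.6 and CT-13 name both periods for the SMWQ.

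This result does not need SAP 10.1. SAP 9.5 and the table list are enough.

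**3. Where a late early-termination form goes**

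- SAP 10.1 covers all efficacy and safety scales, and SAP 9 calls the C-SSRS a safety scale, so the rule reaches it.
- Protocol 3.1 asks for early-termination evaluations as soon as possible. Protocol 3.8.3.3 asks for them at the time of withdrawal. Neither gives a limit in days from the last dose.
- A form more than 3 days after the last dose is therefore possible, and the rule drops it.

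**4. On-drug time such a form can cover**

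The most that can be lost is the scheduled gap since the previous C-SSRS, (later week − earlier week) × 7 days:

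| Stretch | Gap between C-SSRS visits | Days |
|---|---|---|
| Up to Week 2 | 1 week | 7 |
| Weeks 2 to 4 | 2 weeks | 14 |
| Weeks 4 to 20 | 4 weeks | 28 |
| Weeks 20 to 44 | 6 weeks | 42 |
| Weeks 44 to 52 | 8 weeks | 56 |

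These are nominal gaps, before the ±3-day visit windows. A subject who stops partway through a gap loses only the days from the last C-SSRS to the last dose.

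**5. The other route to a table**

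SAP 9.1 includes adverse events up to 30 days after the last dose. An event on an excluded form is tabulated there if the investigator also recorded it as an adverse event. Neither document says that a positive C-SSRS must be so recorded.

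**The case against.** **Scope of SAP 10.1.** Its bracketed list shows AISRS, CGI-S, AIM-A, a CGI change score and one redacted item. It does not visibly name the C-SSRS. Keeping the last observation in each weekly interval also fits by-visit scores better than counts of any occurrence. This stands in part: applying the rule to the C-SSRS needs SAP 9 and 10.1 read together. If the C-SSRS were outside the rule, however, the SAP would give no rule for assigning a late early-termination form.

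**On-drug suicidality.** A reader might infer that suicidality arising on drug never reaches a table. The documents do not support that. All 12 treatment-period visits feed CT-6.1 to CT-6.8, including a Week 52/ET form within 3 days of the last dose. The on-drug loss is confined to late early-termination forms.

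**Events after stopping.** A reader might also infer that these go unreported altogether. That is too strong. Adverse events are collected at all six follow-up contacts and tabulated to 30 days, and serious ones are also listed in CT-9.2. This backstop is real but partial, for the reason in step 5.

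**Timing of the visit.** Protocol 3.8.3.3 ties it to withdrawal, and the schedule gives the Week 52/ET column a ±3-day window. Both make long delays less likely. Neither limits the time from the last dose, since a subject may stop tablets before withdrawing.

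**Labelling.** The trial is single-arm and descriptive, and the C-SSRS summary openly states its period. The issue is incomplete reporting of collected data, not a biased comparison.

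**Conclusion.** The point holds in limited form. The follow-up part follows directly from SAP 9.5 and the table list: 2 of 14 scheduled post-dose forms have no planned C-SSRS output. The early-termination part rests on reading SAP 10.1 with SAP 9. It can hide up to 4, 6 or 8 weeks of on-drug look-back in an affected subject, depending on when dosing stopped.

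The number of subjects affected cannot be computed, because the documents give no distribution of the delay between last dose and early-termination visit. A reader might take 720 − 100 = 620 early endings and apply an assumed late share; 5% to 30% would give 31 to 186 forms. That should not be used as an estimate. Protocol 3.3.1 gives the 100 as an exposure expectation, not a forecast of completers. The Enrolled Sample is everyone who signs consent, some subjects lost to follow-up will have no form at all, and the late share has no source. A dropped form also changes a count only if it holds a finding that no retained form shows.

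The plan should still be changed. Following it as written leaves collected suicidality data out of its own tables, and the remedy is small.

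**What to change.** 1. In SAP 9.5 and 10.1, state that any post-baseline Since Last Visit C-SSRS whose look-back includes at least one dosing day counts as treatment-period data, whatever its date. This would also settle a Day 2 or Day 7 form that is the first one completed after the last dose.
2. Add a separate follow-up-period C-SSRS summary and listing for the Day 2 and Day 7 forms, next to CT-6.1 to CT-6.8, as SAP 9.6 and CT-13 already do for the SMWQ.
3. Leave the 3-day rule in place for the by-visit efficacy summaries.

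The cost is SAP wording and a few table rows, with no new data collection. There is one small downside: some events counted as treatment-period under item 1 may have occurred shortly after the last dose. A footnote giving the form date and the last dose date would let a reader see which ones.

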## 10.2 Scales: Rules for Scoring and Handling of Missing Data

## 10.2.1 Adult ADHD Investigator Symptom Rating Scale (AISRS)

The AISRS is a modified version of the ADHD Rating Scale that reflects the impact and severity of ADHD among adults and will be administered at each scheduled visit in the openlabel treatment period, and at 2 and 7 days after the last dose of IMP in the follow-up period. It is a clinician-administered scale that measures the 18 symptoms of adult ADHD using a Likert scale: 0 (none); 1 (mild); 2 (moderate); and 3 (severe) and uses a semi-structured interview methodology with suggested prompts for each item to improve interrater reliability. The scale's 18 items directly correspond to the 18 DSM-5 symptoms of ADHD where 9 inattentive items alternate with 9 hyperactive impulsive items. The maximum total score for the scale is 54 points, with 27 points for each subscale. The total score is the sum of both the Inattentive and Hyperactive Impulsive subscales.

The AISRS inattentive subscale score and hyperactive-impulsive subscale score, as well as the AISRS total score is set to be missing if more than one item of a subscale is missing for inattentive subscale or hyperactive-impulsive subscale, separately. If one item is missing for a given subscale (inattentive or hyperactive-impulsive), then the subscale score is derived as the

mean of scores from the 8 non-missing items multiplied by 9. All imputed scores are rounded to the first decimal place. The 9 inattentive items consist of the 9 odd numbered items and the 9 hyperactive impulsive items consist of the 9 even numbered items.

## 10.2.2 Clinical Global Impression Severity of Illness Scale – Modified for Attention-Deficit Hyperactivity Disorder

The CGI-S modified is an observer-rated scale that will be used to measure symptom severity. To perform this assessment, the investigator or rater will respond to the following question: "Considering your total clinical experience with adult ADHD, how mentally ill is the patient at this time?" Response choices include: 1 = normal, not at all ill; 2 = borderline mentally ill;3 = mildly ill; 4 = moderately ill; 5 = markedly ill; 6 = severely ill; and 7 = among the most extremely ill patients. CGI-S is assessed at each scheduled visit in the open-label treatment period.

## 10.2.3 Attention-Deficit Hyperactivity Disorder Impact Module – Adult (AIM-A)

The AIM-A is a subject self-report questionnaire which assesses quality of life in adults with ADHD. The questionnaire has 4 global quality of life items, 5 economic impact items, and 5 multi-item scales that assess the following key concepts: Living with ADHD, General Well-Being, Work, Home and School Performance and Daily Functioning. Additionally, Relationships and Communication, and Impact of Symptoms are also included.

## 10.2.4 Study Medication Withdrawal Questionnaire (SMWQ)

The SMWQ is a questionnaire to assess withdrawal symptoms. The SMWQ is a modification of the Amphetamine Withdrawal Questionnaire in which the terms "amphetamines and methamphetamine" are replaced with the term "the study medication." The SMWQ is assessed at Week 52/ET in the open-label treatment period and at 1, 2, 3, 5, 7, and 10 days after the last dose of IMP in the follow-up period.

# 10.2.5 Columbia-Suicide Severity Rating Scale (C-SSRS)

Suicidality will be monitored during the trial using the C-SSRS. The C-SSRS is a semistructured interview that captures the occurrence, severity, and frequency of suicide-related thoughts and behaviors during the assessment period. The interview includes definitions and suggested questions to solicit the type of information needed to determine if a suicide-related thought or behavior has occurred. The interview and rating for the C-SSRS must be completed by a licensed clinician who has been successfully trained to rate this scale by the sponsor or a designee and is medically responsible for the subject. Documentation of trial training should be maintained in the investigational site's files.

This trial will use the "Baseline/Screening" and "Since Last Visit" versions of the scale. The "Baseline/Screening" version, which assesses the life-time experience of the subject with suicide events and suicidal ideation and the occurrence of suicide events or ideation within a specified time period prior to entry into the trial, will be completed for all de novo subjects at the screening visit to determine the eligibility. Any subject with active suicidal ideation within the last 30 days, suicidal behaviors within the last year, or who in the clinical judgment of the investigator presents a serious risk of suicide should be excluded from the trial. The "Since Last Visit" C-SSRS form will be completed at all other in-clinic visits for all subjects (rollover and de novo).

The C-SSRS is assessed at each scheduled visit in the screening period (for de novo subjects), the open-label treatment period and at 2 and 7 days after the last dose of IMP in the follow-up period.

# **11 Potential Clinical Relevance Criteria from Protocol**

Appendix 1 C	Criteria for Identifying Vital Signs of Potential Clinical Relevan			
Variable	Criterion Value a	Change Relative to Baseline a		
Heart Rate b	> 100 bpm < 50 bpm	≥ 10 bpm increase ≥ 10 bpm decrease		
Systolic Blood Pressure b	≥ 140 mmHg < 90 mmHg	≥ 20 mmHg increase ≥ 20 mmHg decrease		
Diastolic Blood Pressure b	≥ 90 mmHg < 60 mmHg	$\geq$ 10 mmHg increase $\geq$ 10 mmHg decrease		
Orthostatic Hypotension	
 
≥ 30 mmHg decrease in systolic blood pressure and/or a ≥ 20 mmHg
 
in diastolic blood pressure after at least
 
3 minutes of standing compared to the previous supine blood pressure.
 
	Not Applicable (baseline status not considered)		
Orthostatic Tachycardia	≥ 25 bpm increase in heart rate from supine to standing	Not Applicable (baseline status not considered)		
Weight	-	≥ 7% increase ≥ 7% decrease		

a In order to be identified as potentially clinically relevant, an on-treatment value must meet the "Criterion Value" and also represent a change from the subject's baseline value of at least the magnitude shown in the "Change Relative to Baseline" column.

b As defined in "Supplementary Suggestions for Preparing an Integrated Summary of Safety Information in an Original NDA Submission and for Organizing Information in Periodic Safety Updates," FDA Division of Neuropharmacological Drug Products draft (2/27/87).

Relevance			
Laboratory Tests	Criteria		
Chemistry			
AST (SGOT)	$\geq$ 3 x upper limit of normal (ULN)		
ALT (SGPT)	$\geq 3 \text{ x ULN}$		
Alkaline phosphatase	$\geq$ 3 x ULN		
BUN	$\geq$ 30 mg/dL		
Creatinine	$\geq 2.0 \text{ mg/dL}$		
Uric Acid	-		
Men	$\geq 10.5 \text{ mg/dL}$		
Women	$\geq 8.5 \text{ mg/dL}$		
Bilirubin (total)	$\geq 2.0 \text{ mg/dL}$		
Creatine Phosphokinase (CPK)	> 3  x ULN		
Hematology			
Hematocrit			
Men	$\leq$ 37 % and decrease of $\geq$ 3 percentage points from Baseline		
Women	$\leq$ 32 % and decrease of $\geq$ 3 percentage points from Baseline		
Hemoglobin			
Men	$\leq 11.5 \text{ g/dL}$		
Women	$\leq$ 9.5 g/dL		
White blood count	$\leq 2,800/$ mm  or $\geq 16,000/$ mm 		
Eosinophils	≥ 10%		
Neutrophils	$\leq 15\%$		
Absolute neutrophil count	$\leq$ 1,500/ mm 		
Platelet count	$\leq$ 75,000/ mm  or $\geq$ 700,000/ mm 		
Urinalysis			
Protein	Increase of $\geq 2$ units		
Glucose	Increase of $\geq 2$ units		
Additional Criteria			
Chloride	$\leq$ 90 mEq/L or $\geq$ 118 mEq/L		
Potassium	$\leq 2.5 \text{ mEq/L}$ or $\geq 6.5 \text{ mEq/L}$		
Sodium	$\leq 126 \text{ mEq/L}$ or $\geq 156 \text{ mEq/L}$		
Calcium	$\leq 8.2 \text{ mg/dL} \text{ or} \geq 12 \text{ mg/dL}$		
Glucose			
Fasting	$\geq 100 \text{ mg/dL}$		
Non-Fasting	$\geq 200 \text{ mg/dL}$		
Total Cholesterol, Fasting	$\geq 240 \text{ mg/dL}$		
LDL Cholesterol, Fasting	$\geq 160 \text{ mg/dL}$		
HDL Cholesterol, Fasting	-		
Men	< 40 mg/dL		
Women	< 50  mg/dL		
Triglycerides, Fasting	$\geq 150 \text{ mg/dL}$		

#### Appendix 2 Criteria for Identifying Laboratory Values of Potential Clinical Relevance

Appendix 3	Criteria for Identifying ECG Measurements of Potential Clinical
Relevance	

Variable	Criterion Value a	Change Relative to Baseline a
Rate		
Tachycardia	≥ 120 bpm	increase of $\geq 15$ bpm
Bradycardia	$\leq 50 \text{ bpm}$	decrease of $\geq 15$ bpm
Rhythm		
Sinus tachycardia b	$\geq 120 \text{ bpm}$	increase of $\geq 15$ bpm
Sinus bradycardia c	$\leq 50 \text{ bpm}$	decrease of $\geq 15$ bpm
Supraventricular premature beat	all	not present $\rightarrow$ present
Ventricular premature beat	all	not present $\rightarrow$ present
Supraventricular tachycardia	all	not present $\rightarrow$ present
Ventricular tachycardia	all	not present $\rightarrow$ present
Atrial fibrillation	all	not present $\rightarrow$ present
Atrial flutter	all	not present $\rightarrow$ present
Conduction		
1° atrioventricular block	$PR \ge 200 \text{ msec}$	increase of $\geq 50$ msec
2° atrioventricular block	all	not present $\rightarrow$ present
3° atrioventricular block	all	not present $\rightarrow$ present
Left bundle-branch block	all	not present $\rightarrow$ present
Right bundle-branch block	all	not present $\rightarrow$ present
Pre-excitation syndrome	all	not present $\rightarrow$ present
Other intraventricular conduction block d	$QRS \ge 120 \text{ msec}$	increase of $\geq 20$ msec
Infarction		
Acute or subacute	all	not present $\rightarrow$ present
Old	all	not present $\rightarrow$ present
		$\geq$ 12 weeks post study entry
ST/T Morphological		
Myocardial Ischemia	all	not present $\rightarrow$ present
Symmetrical T-wave inversion	all	not present $\rightarrow$ present
Increase in QTc	$QTcF \ge 450 \text{ msec}$	
	(men) $OT_{a}E > 470 maga$	
	(women)	

a In order to be identified as potentially clinically relevant, an on-treatment value must meet the "Criterion Value" and also represent a change from the subject's baseline value of at least the magnitude shown in the "Change Relative to Baseline" column.

b No current diagnosis of supraventricular tachycardia, ventricular tachycardia, atrial fibrillation, atrial flutter, or other rhythm abnormality.

c No current diagnosis of atrial fibrillation, atrial flutter, or other rhythm abnormality.

d No current diagnosis of left bundle branch block or right bundle branch block.

